7.1. Discontinuation of Study Intervention

In rare instances, it may be necessary for a participant to permanently discontinue study intervention earlier than the protocol planned duration. Stopping the study intervention may be initiated by either the participant's parent(s)/legal guardian or the Investigator. The Investigator should discontinue the study intervention if the participant experiences intolerable AEs, or if the Investigator believes that continuing dosing would result in an unfavorable risk/benefit for the trial participant. If study intervention is permanently discontinued, the participant will remain in the study to be evaluated for safety and weight change.

Refer to the SoA (Table 2) for data to be collected at the time of discontinuation of study intervention for any reason.

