7.3 Efficacy Measures

The following endpoints will be analyzed for primary efficacy analysis:

• Change in WAZ from baseline to Day 56 visit in the Bi-26 group.

For the secondary endpoints the following will be analyzed:

- Change in weight (in grams) from baseline to Day 56 visit in the Bi-26 group.
- Change in WAZ over time from baseline to Day 90 visit (longitudinal assessment) by duration of dosing.
- Proportion of infants with a $\geq 0.3, \geq 0.4$, and ≥ 0.5 change in WAZ from baseline (Day 1) to Day 56 visit.
- Proportion of infants with WAZ > 2 at Day 56 visit.
- Proportion of re-hospitalizations for acute non-surgical illness through Day 56 visit.
- Presence of *B. infantis* in engraftment stool samples on Days 1, 28, 56, and 90.

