8.1.5 Per-Protocol (PP) Population

All participants randomly assigned to study intervention, who received the study intervention, have a Day 90 visit, and did not substantially deviate from the protocol procedures. Important protocol deviations will be evaluated individually by the sponsor to decide whether it has basis to exclude a participant from the PP population. Deviation from study intervention compliance (see Section 11.4) is defined as compliance of less than 80%. Participants will be analyzed according to the intervention they actually received (for details refer to Section 11.1).

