10 OVERALL STATISTICAL CONSIDERATIONS

10.1 General Conventions

Descriptive statistics will be presented for continuous data with applicable decimal precision as follows in relation to the source data (indicated as N+x), with a maximum of 3 decimals to be displayed:

- Number (N).
- Mean, (N+1).
- Number of missing observations, (N).
- Standard deviation (SD), (N+1).
- Median, (N+1).
- Minimum, (N+1).
- Maximum, (N+1).

Absolute and relative frequencies will be used to describe categorical variables. Unless otherwise specified, the denominators for percentages will be the number of participants in each intervention group with non-missing data for the variable of interest at the summarized visit. Percentages will be presented with 1 decimal place and a percent sign (%).

All statistical testing will be 2-sided and performed at the 0.05 level. When reporting the results of significance tests p-values will be reported. All confidence intervals will be 2-sided at the 95% level, unless otherwise stated.

Study day is calculated relative to the first study intervention administration on Day 1.

Confidential Page 22 of 50

- If the current ACR date is after study intervention administration: Study Day = (Current ACR Date – Study Intervention administration Date) + 1
- If the current ACR date is before study intervention administration:

Study Day = (Current ACR Date – Study Intervention administration Date)

Study day will not be calculated if either the current ACR or the study intervention administration date is incomplete or missing.

The following periods for the study are defined:

- Treatment Period: Day 1 through last dose of participant.
- Follow-up Period: Day of last dose of participant + 1 up to EoS.

SAS® code of SAS® procedures that will be used to perform efficacy and safety analyses is provided in Appendix 3.

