11.4 Study Intervention Compliance and Exposure

Participant compliance with study intervention will be assessed at each visit. Compliance will be assessed by counting returned doses, and by asking the mother if her infant received a dose each day, and if any of the additional doses were administered and why. Deviations from the planned dosing regimen will be recorded in the eCRF.

The compliance is defined as

$$CS = 100 \times \frac{Number\ of\ doses\ administered}{Number\ of\ days\ on\ study\ intervention}\%$$

where

- Number of doses administered: is the actual number of doses administered as per exposure eCRF. If a dose was re-administered due to vomiting within 30 minutes/spitting out the dose will be counted as one dose. Deviations from planned dosing regimen will be used to consider if doses were used but not administered for any reason. According to the CRF completion guidelines, doses that were spilled without any part administered, were recorded as zero doses used. If a second dose was used and administered on the same day, it was recorded in a second record in the database.
- Number of days on study intervention: calculated as the number of days during the treatment period which participant could have received treatment. Days on which treatment/study was discontinued does not form part of denominator.

Descriptive statistics of the compliance will be summarized in a table by treatment group and visit (Day 7, 14, 21, 28, Combined Day 1 to 28). For weekly summaries, compliance is calculated based on the period between the preceding visit and the current. The frequency and percentage of participants who achieved 100% compliance score over the entire treatment period will be presented by treatment group in the same table.

The number of doses administered will be presented in a separate table using descriptive statistics (mean, SD, median, min, max) by treatment group and visit. Additionally, the number and percentage of participants will be presented in the same table according to the following intervals for doses administered:

- 28 doses (100% of doses taken)
- 14 to 28
- < 14

The proportion of infants who had x% of doses for each of the dose administer and reconstitution scenarios (see Section 11.4.2), including partial doses, doses mixed in breastmilk, doses mixed in water and doses vomited within 30 minutes of administration, will be summarized using summary statistics in a table by treatment according to the following categories:

- 100%

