11.5.4 Secondary outcome: Change over time in WAZ by duration of dosing

11.5.4.1 Analysis of endpoint

The difference in the change over time will be represented as the estimated difference in CFB at Day 90 using the results generated by the model as described in Section 11.5.2.1 for the PP population.

In order to take duration of dosing into account, the model described above will be adjusted by study intervention compliance (see Section 11.4) and presented in separate tables for the mITT and PP populations.

11.5.5 Secondary outcome: Proportion of infants with increase in WAZ ≥ 0.3 , 0.4 and 0.5 at Day 56

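### The SAP compliance score stays at 100% for an infant dosed daily until an early stop, so it cannot represent duration of dosing, and the 80% Per-Protocol rule does not flag early stopping

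*SAP*

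**What the plan says.** **The score.** SAP 11.4 divides doses administered by days on study intervention. The denominator is "calculated as the number of days during the treatment period which participant could have received treatment", and "Days on which treatment/study was discontinued does not form part of denominator". SAP 10.1 defines the period: "Treatment Period: Day 1 through last dose of participant". Elsewhere in 11.4, however, the compliance histogram labels the treatment period as Day 1 to 28, and the summary table has a combined Day 1 to 28 entry.

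**Its use for duration.** SAP 7.3 lists the secondary endpoint "Change in WAZ over time from baseline to Day 90 visit (longitudinal assessment) by duration of dosing". SAP 11.5.4.1 implements it as follows: "In order to take duration of dosing into account, the model described above will be adjusted by study intervention compliance".

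**Its use for PP.** Under SAP 8.1.5 a compliance deviation "is defined as compliance of less than 80"%. The same section adds: "Important protocol deviations will be evaluated individually by the sponsor to decide whether it has basis to exclude a participant from the PP population". Protocol 7.1 keeps early stoppers under observation: "If study intervention is permanently discontinued, the participant will remain in the study to be evaluated for safety and weight change".

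**The PP visit rule.** Protocol 9.5 and SAP 8.1.5 both require a Day 90 visit for PP. SAP 11.5.2.4.1 repeats the primary model in PP, and that model (11.5.2.1) is fitted jointly to Days 28, 56 and 90 although the primary contrast is at Day 56.

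**The concern.** A score limited to time on treatment is a legitimate measure of adherence. The difficulty is what the SAP asks of it in two places.

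- **Duration.** If the denominator stops when dosing stops, length of dosing cancels out of the ratio. Adjusting by it cannot answer a secondary question about duration among infants who missed no day.
- **PP.** The 80% rule is the only numerical test of whether an infant received the planned course. An early stopper can stay in follow-up, attend Day 90 and meet the rule after very few doses, while an infant with far more doses is flagged.

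At stake are the duration-of-dosing analysis and the PP sensitivity analyses. The Day 90 visit requirement is a separate, smaller mismatch: an infant with a valid Day 56 weight can leave a Day 56 sensitivity analysis because of something that happened later.

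**Working it through.** The documents report no compliance result to reproduce. The one anchor is that SAP 11.4 equates 28 doses with the full course.

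**Inputs.** One planned dose per day for 28 days (Protocol 6); treatment period from Day 1 to the infant's last dose (SAP 10.1); discontinued days removed (SAP 11.4); threshold 80% (SAP 8.1.5).

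**Formulas.** SAP score = 100 × doses administered / days on study intervention. Share of planned course = 100 × doses administered / 28. For daily dosing with last dose on Day k, the SAP score is 100 × k/k = 100% for every k from 1 to 28.

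| Pattern | SAP score | Share of planned course | Flagged by the SAP's 80% rule? |
|---|---|---|---|
| 1 dose, then stop | 1/1 = 100% | 1/28 = 3.6% | No |
| 3 daily doses, then stop | 3/3 = 100% | 3/28 = 10.7% | No |
| 14 daily doses, then stop | 14/14 = 100% | 14/28 = 50.0% | No |
| 22 daily doses, then stop | 22/22 = 100% | 22/28 = 78.6% | No |
| 22 doses, 6 days missed, last dose Day 28 | 22/28 = 78.6% | 22/28 = 78.6% | Yes |
| 27 daily doses, then stop | 27/27 = 100% | 27/28 = 96.4% | No |

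The two rows with 22 doses have the same exposure and opposite results. The 3-dose row is not flagged while a 22-dose row is, so the rule can rank infants against their exposure.

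**Does the Day 1 to 28 label change this?** Take an infant dosed daily through Day 7 and then stopped.

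- Period fixed at 28 days, only the single stop day removed: 7/27 = 25.9%, flagged. On this reading 21 doses give 21/27 = 77.8% (flagged) and 22 give 22/27 = 81.5% (not flagged).
- Period fixed at 28 days, all 21 days after the stop removed: 7/(28 − 21) = 7/7 = 100%, not flagged.
- SAP 10.1 definition: 7/7 = 100%, not flagged.

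The SAP 10.1 definition, the restriction to days on which the infant could have been treated, and the discontinuation sentence all favour 100%. The label leaves the denominator ambiguous, and the choice can reverse the flag.

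**With a fixed base of 28.** 0.80 × 28 = 22.4, so 23 doses (82.1%) pass and 22 (78.6%) fail, whatever the pattern.

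**The case against.** **PP does not rest on the score alone.** Below 80% is a deviation, not an automatic exclusion. SAP 8.1.5 provides individual sponsor review of important deviations, SAP 8.1 requires agreement on the PP set before lock and unblinding, and Protocol 9.6 adds a blinded review of violators and exclusions. This stands. A reader might infer that a 3-dose infant necessarily enters PP; the documents show only that it passes the score. What remains is that neither document states a criterion for early stopping, so the decision is left to case-by-case judgement.

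**Early stopping is expected to be rare and is reported elsewhere.** Protocol 7.1 anticipates it only rarely, and disposition (SAP 11.1) and the dose-count tables and histogram (SAP 11.4) will show it. This limits the size of the problem. But those outputs feed neither the PP rule nor the duration model.

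**Other uses of the score.** A reader might extend the criticism to the compliance correlation (SAP 11.5.2.3), the candidate confounder list (11.5.2.4.2) or the subgroup with all doses received (8.2). The first two are presented as analyses of compliance, not duration, and for the third SAP 11.4 already equates all doses taken with 28. At most a cross-reference is missing. The differing population labels for WAZ over time are also not a separate fault: the mITT Day 90 contrast is produced under 11.5.2.1, and Table 8 lists the compliance-adjusted model for both mITT and PP.

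**The Day 90 rule is consistent across both documents** and suits an endpoint that runs to Day 90. This is fair for the Day 90 contrast. It does not justify the rule for Day 56 analyses.

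**Conclusion.** The point holds on the SAP's formal definitions and should be fixed before unblinding. Among daily dosers the score is 100% at every length of dosing while the share of the planned course runs from 3.6% to 100%. The adjustment in 11.5.4.1 therefore does not take duration into account for these infants, and the 80% rule does not flag early stopping. This assumes the SAP 10.1 treatment period; the competing Day 1 to 28 label is a further reason to state one denominator.

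A reader might infer that the main efficacy result is compromised. It is not: the mITT primary and key secondary models do not use the score or the PP set. The number of early stoppers cannot be computed from the documents and is expected to be small.

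The Day 90 visit rule is a real but secondary mismatch. A reader might try to size it from the planned 10% loss and 3% mortality, but the documents give no timing for either, so the number with Day 56 data and no Day 90 visit cannot be derived and could be zero.

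**What to change.** 1. **Denominator.** State one definition in SAP 11.4 and align the SAP 10.1 period and the Day 1 to 28 labels with it.
2. **SAP 11.5.4.1.** Replace the compliance score with the number of doses administered or the days from first to last dose. Do this mainly in mITT, because under item 3 a PP infant who met the criterion would have only 23 to 28 doses. Interpret it descriptively, because it is measured after randomization.
3. **PP criterion.** Use 100 × doses administered / 28 planned dosing days for the 80% rule. Keep the while-on-treatment score as a descriptive adherence measure.
4. **PP visit rule.** For Day 56 PP analyses require the Day 56 visit, and fit the PP model for that contrast with this flag and all available visits. Keep the Day 90 flag for the Day 90 contrast. Record the departure from Protocol 9.5 in SAP 9.

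**Cost.** SAP wording, one changed derivation, a second PP flag and a second run of the PP model, with no new data. The PP set may change slightly. With a fixed base of 28, stopping for any reason counts as low compliance, which is why the existing score should be reported alongside.

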| Objectives | Endpoints |
|---------------------------------------------------------------------------------------------------------|---------------------------------------------------------------------------------------------------------------------------|
| Primary | |
| To evaluate the change in weight (standardized for age) of infants receiving Bi-26 | WAZ change from baseline (Day 1) to the Day 56 visit in Bi-26 group |
| Key Secondary | |
| To evaluate the change in weight of infants receiving Bi-26 | Change in weight (in grams) from baseline (Day 1) to the Day 56 visit in the Bi-26 group |
| Other Secondary | |
| To estimate the treatment response over time associated with Bi-26 | WAZ change from baseline (Day 1) over time through the Day 90 visit (longitudinal assessment) by duration of dosing |
| To assess the proportion of infants who achieve a specified change in WAZ from baseline to Day 56 | Proportion of infants with $a \ge 0.3, \ge 0.4$, and ≥ 0.5 change in WAZ from baseline (Day 1) to Day 56 visit |
| To assess the proportion of infants who achieve a specified WAZ at Day 56 | Proportion of infants who achieve a WAZ > -2 at Day 56 visit |
| To assess the re-hospitalization rate | Number of re-hospitalizations for acute non-surgical illness through the Day 56 visit |
| To assess the safety of Bi-26 supplementation through End of Study (EoS, Day 90 visit) | Number of adverse events (AEs) and serious adverse events (SAEs) through Day 90 |
| To measure engraftment of B. infantis in participants | Presence of B. infantis in stool on Days 1, 28, 56, and 90 |

| Objectives | Endpoints |
|------------------------------------------------------------------------------------------------------------------------------|----------------------------------------|
| Exploratory | |
| To describe stool biomarkers in response to Bi-26 supplementation in terms of stool composition (e.g., microbiome, pH) | Stool biomarkers on Days 1, 28, and 56 |
| To describe the blood biomarkers (e.g., inflammation, metabolomics), in response to Bi-26 supplementation | Blood biomarkers on Days 1 and 28 |

Table 2: Schedule of Activities (SoA)

| Activities | | Clinic Visit 1 | | Homo Visits | e 5 | Clinic Visit 2 | Home Visit | Home Visit | Home Visit | Clinic Visit 3 | Clinic Visit 4 | Discon Visit ^b |

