5.3. Screen Failures

A screen failure participant is defined as a participant whose parent(s)/legal guardian consented to participate in the clinical study, but the infant is not subsequently randomly assigned to group and study intervention on the Day 1 visit.

A minimal set of screen failure information is required to ensure transparent reporting of screen failure participants to meet the Consolidated Standards of Reporting Trials (CONSORT) publishing requirements and to respond to queries from regulatory authorities. Minimal information includes demography, screen failure details, eligibility criteria, and any SAE.

Infants who do not meet the eligibility criteria for participation in this study (screen failures) will not be rescreened. Infants whose screening visit is outside of the 7-day planned window, due to a delay in hospital discharge, may be rescreened and enrolled if all the eligibility criteria are met.

6. Study Intervention

Study intervention is defined as any investigational intervention, marketed product or placebo, intended to be administered to a study participant according to the study protocol. The study intervention includes Bi-26 and placebo, given to approximately 198 participants, per group.

All participants will be given either Bi-26 supplementation, or product matched placebo (lacking the active ingredient), based on randomization (refer to Section 6.2). A single dose (Bi-26 or placebo control) will be resuspended, and administered to each participant, daily, for 28 days. Participants will be monitored for 30 minutes, and a repeat dose will be administered if a participant vomits within this observation period.

While a total of 7 doses are to be administered to the participant per week for a total of 4 weeks, 2 additional doses will be supplied each week to account for repeat dose administration in the event of vomiting, or unexpected events which may render a dose unusable (e.g., spillage or otherwise compromised). Therefore, mothers will be dispensed 9 doses containing Bi-26 or placebo once a week, within 2 days before the doses are needed to ensure that doses are available when needed. Doses will either 1) be delivered to the mother by study staff, or 2) stored by staff, at the local health center to be picked up from the health center.

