10.2.1. Definition of AE

AE Definition

An AE is any untoward medical occurrence in a patient or clinical study participant, temporally associated with the use of study intervention, whether or not considered related to the study intervention.

NOTE: An AE can therefore be any unfavorable and unintended sign (including an abnormal laboratory finding), symptom, or disease (new or exacerbated) temporally associated with the use of study intervention.

Events Meeting the AE Definition

Any abnormal laboratory test results (hematology, clinical chemistry, or urinalysis) or other safety assessments (e.g., ECG, radiological scans, vital signs measurements), including those that worsen from baseline, considered clinically significant in the medical and scientific judgment of the investigator (i.e., not related to progression of underlying disease).

Exacerbation of a chronic or intermittent pre-existing condition including either an increase in frequency and/or intensity of the condition.

New conditions detected or diagnosed after study intervention administration even though it may have been present before the start of the study.

Signs, symptoms, or the clinical sequelae of a suspected drug-drug interaction.

Signs, symptoms, or the clinical sequelae of a suspected overdose of either study intervention or a concomitant medication. Overdose per se will not be reported as an AE/SAE unless it is

an intentional overdose taken with possible suicidal/self-harming intent. Such overdoses should be reported regardless of sequelae.

Events **NOT** Meeting the AE Definition

Any clinically significant abnormal laboratory findings or other abnormal safety assessments which are associated with the underlying disease, unless judged by the investigator to be more severe than expected for the participant's condition.

The disease/disorder being studied or expected progression, signs, or symptoms of the disease/disorder being studied, unless more severe than expected for the participant's condition.

Medical or surgical procedure (e.g., endoscopy, appendectomy): the condition that leads to the procedure is the AE.

Situations in which an untoward medical occurrence did not occur (social and/or convenience admission to a hospital).

Anticipated day-to-day fluctuations of pre-existing disease(s) or condition(s) present or detected at the start of the study that do not worsen.

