- 75% to 99%

Confidential Page 29 of 50

- 50% to 74%
- 25% to 49%
- < 25%

A histogram of compliance scores will be presented by treatment group for the compliance scores across the treatment period (Day 1 to 28). An additional histogram by treatment group will be presented for number of doses administered.

The exposure listing will include date of study intervention administration, whether the dose is the first dose or the last, deviations from planned dosing regimen, reason for non-compliance, what study powder was mixed in, vomiting after intake of study intervention and whether or not a second dose was administered following vomiting.

Another listing will be provided with compliance scores across weekly intervals during the treatment period, as well as over the entire treatment period. It includes the start date of the interval for which compliance is calculated, number of days on treatment in interval, number of doses of study intervention used, number of doses vomited within 30 minutes, number of doses administered and the calculated compliance.

The Safety population will be used for the table summaries. The summary of study intervention compliance table will also be presented for the mITT population. Listings will be presented for the mITT population.

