11.4.2 Infant Feeding Diary Card

The IFDC captures information about the feeding the infant received on a particular study day through the Day 90 visit, which includes the following for each day:

- Number of breastmilk feedings
- Number of formula feedings
- Number of solid food feedings

Confidential Page 30 of 50

- Number of other feedings
- Total number of feedings

as well as info on whether or not the infant got all of the mixed study powder in, how the study powder was re-constituted and if vomiting occurred after administration of study intervention.

For each participant the proportion of feedings from breastmilk through the Day 56 Visit will be calculated as follows:

$$Prop\ breastmilk\ feedings = \frac{Sum\ of\ \#\ BM\ feedings\ per\ day}{Sum\ of\ \#\ Total\ feedings\ per\ day}$$

for available data up to Day 56 visit. Days with missing values in feeding information will not contribute to the above calculation.

The proportion of infants who had x% of feedings from breastmilk through the Day 56 visit will be summarized using summary statistics in a table by treatment according to the following categories:

- 100%
- 75% to 99%
- 50% to 74%
- 25% to 49%
- < 25%

A diary card entry on any given day is non-compliant, if no values were recorded for the feeding information and the total number of feedings for the day was missing. The proportion of infants who had x% of compliant entries will be presented by treatment group according to the following categories:

- 100%
- 75% to 99%
- 50% to 74%
- 25% to 49%
- < 25%.

Infant diary card results will be listed for the safety population. The listing will include whether diary card was returned, date of distribution, date of receipt, number of feedings for each type and the total.

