11.6.1 Adverse Events

Safety assessments include SAEs and AEs from the time the ICF is signed through Day 90 (or at the date of last visit/study discontinuation).

An AE is considered treatment emergent if it started on or after the date of first dose of study intervention administration.

Confidential Page 37 of 50

An AE overview table containing the number and percentage (expressed in percent) of participants with AEs from Day 1 through Day 90 will be summarized by treatment group for the following:

- Any AE
- Any TEAE
- TEAEs related to study intervention
- TEAEs by maximum severity (Mild, Moderate and Severe)
- TEAEs leading to study intervention discontinuation
- TEAEs leading to study withdrawal
- Serious TEAEs
- Serious TEAEs with Outcome of Death

Additionally, the number and percentage of participants with AEs will be provided by SOC and PT and by treatment group for the following:

- Any TEAE
- TEAEs by maximum severity
- TEAEs related to study intervention
- Serious TEAEs
- Serious TEAEs related to study intervention

By-period summaries will be presented for TEAE and serious TEAEs by treatment group, where period is defined as in Section 10.1.

The overall AE summary table, AE table by SOC and PT and SAE table by SOC and PT will be presented by subgroups as specified in Section 8.2.

All AEs and SAEs will be classified according to the latest version of MedDRA.

SOC and PT will be sorted alphabetically by SOC and by decreasing frequency of preferred term in the all Bi-26 group (then alphabetically for ties). If a participant has more than one AE at a given level (eg, SOC and preferred term), the participant will only be counted once within that level. All summary tables will include the number of AEs. Missing severities and relationship will not be regarded as 'worst case'.

The following listings will be presented:

- All AEs through to Day 90
- SAEs through to Day 90

The AE listing by participant will display all reported AEs up to Day 90 and will include the verbatim term in addition to the SOC and preferred term. This listing will also include all relevant data associated with the event: eg, date of onset, date resolved, date of first dose, date of last dose, severity, whether AE is serious, outcome, relationship to study intervention, action taken with study intervention, and required therapy. When a date is presented, the study day

Confidential Page 38 of 50

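### SAP 11.4 puts 0 to 6 vomited doses out of 28 in one class, so its by-arm vomiting table can miss a difference in infrequent vomiting

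*SAP*

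**What the plan says.** SAP 11.4 (Study Intervention Compliance and Exposure) takes four features of dosing. Two are incomplete intake of a dose and mixing with breastmilk. For the other two the text reads: "doses mixed in water and doses vomited within 30 minutes of administration, will be summarized using summary statistics in a table by treatment". One set of classes serves all four: 100%, 75 to 99%, 50 to 74%, 25 to 49%, and under 25% of the infant's doses. The tables in 11.4 use the Safety population.

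Vomiting is planned for elsewhere as follows:

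- Protocol section 6 (Study Intervention): "Participants will be monitored for 30 minutes, and a repeat dose will be administered if a participant vomits within this observation period".
- SAP 11.4.2: the diary card records "if vomiting occurred after administration of study intervention".
- SAP 11.4, definition of doses administered: "If a dose was re-administered due to vomiting within 30 minutes/spitting out the dose will be counted as one dose".
- SAP 11.4, compliance listing by weekly interval: "number of doses vomited within 30 minutes, number of doses administered and the calculated compliance". A separate exposure listing shows vomiting dose by dose.
- SAP 11.6.1: treatment-emergent adverse events (TEAEs) by system organ class, preferred term and arm, where "All summary tables will include the number of AEs".

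**The concern.** The classes suit the breastmilk and water rows, where an infant can plausibly sit anywhere from 0 to 100%. They do not suit an event that may affect only a few doses per infant. Four of the five classes need at least a quarter of all doses to be vomited, and none separates infants who never vomited from those who did.

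No other by-arm output fills the gap completely. The compliance and dose-count tables do not show vomiting, because a dose repeated after vomiting counts once. Exact vomit counts appear only in per-participant listings. TEAE tables show vomiting only where it was recorded as an AE, and they do not separate the 30 minutes after a dose.

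The protocol builds in a 30-minute watch, repeat dosing and spare doses partly because of vomiting. How many infants vomited a dose at all, by arm, is therefore a basic tolerability question in recently hospitalized, underweight infants. The one table dedicated to post-dose vomiting may not answer it. The partial-dose row has the same display problem, though only as a matter of dose delivery.

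**Working it through.** **Inputs.** From the documents: 28 planned doses per infant, the five classes of SAP 11.4, and 198 infants randomized per arm (Protocol 9.4, SAP 7.1.3). Neither document gives a vomiting rate, so there is no planned figure to reproduce. The per-dose rates, the doubling between arms and the intraclass correlation (ICC) within infants are assumptions.

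**Step 1: what the lowest class contains.** 0/28 = 0.0%, 6/28 = 21.4%, 7/28 = 25.0%. So 0 to 6 vomited doses fall under 25%, and 7 is the first count outside. If all 36 supplied doses (9 per week for 4 weeks) were the denominator, 8/36 = 22.2%, and 0 to 8 would share the class.

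**Step 2: model.** Let X be the number of vomited doses out of 28.

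- Independent doses: X is binomial(28, p), so P(any) = 1 − (1 − p)^28.
- Vomiting clustered within infants: X is beta-binomial with a = p(1 − ICC)/ICC and b = (1 − p)(1 − ICC)/ICC. At ICC 0.1, a = 9p and b = 9(1 − p).
- The class under 25% holds P(X ≤ 6). Any vomiting is P(X ≥ 1).
- To gauge how visible a contrast is: z = (p2 − p1) / √(2·p̄(1 − p̄)/198), where p̄ is the mean of the two proportions.

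**Step 3: results at ICC 0.1, 198 infants per arm.**

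| Per-dose rate | Share under 25% | Infants outside it | z | Any vomited dose | z |
|---|---|---|---|---|---|
| 1% vs 2% | 99.4% vs 98.7% | 1.1 vs 2.5 | 0.7 | 12% vs 23% (24 vs 46 infants) | 2.8 |
| 2% vs 4% | 98.7% vs 96.9% | 2.5 vs 6.1 | 1.2 | 23% vs 41% (46 vs 81 infants) | 3.8 |
| 5% vs 10% | 95.8% vs 88.0% | 8 vs 24 | 2.8 | 49% vs 74% | 5.2 |

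First row worked through for any vomiting: p̄ = (0.1232 + 0.2318)/2 = 0.1775, the standard error is √(2 × 0.1775 × 0.8225/198) = 0.0384, and z = 0.1086/0.0384 = 2.8.

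**Step 4: other degrees of clustering.**

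- Independent doses, 1% vs 2%: 100.0% vs 100.0% fall under 25%, while any vomiting is 1 − 0.99^28 = 25% vs 1 − 0.98^28 = 43%.
- Independent doses, 5% vs 10%: 99.96% vs 98.2% under 25%, and any vomiting 76% vs 95%.
- ICC 0.4, 1% vs 2%: z = 1.0 for the planned classes, against 1.8 for any vomiting (4.9% vs 9.5%).

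Any-versus-none shows more than the planned classes in every case. The loss is largest when vomiting is infrequent and weakly clustered. It shrinks as vomiting becomes more frequent or more concentrated in a few infants.

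**The case against.** The strongest reply is that this is an exposure table, not a safety analysis. Vomiting sits in 11.4 because it triggers a repeat dose. For dose delivery the useful question is which infants lost a material share of doses, and the classes answer that. Safety is assessed through the endpoint "Number of adverse events (AEs) and serious adverse events (SAEs) through Day 90". Vomiting fits the protocol's definition: "An AE is any untoward medical occurrence in a patient or clinical study participant, temporally associated with the use of study intervention". Protocol 8.4 makes the investigator responsible for recording events that meet it, and the schedule puts diary review and AE recording at the same visits. SAP 11.6.1 then gives infants and event counts by preferred term and arm, with a separate summary for the treatment period. No data are lost, since exact counts are in listings and any-versus-none could be tabulated at any time. The rates above are assumed, and no test is planned on this table.

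Much of this stands. AE tables cover vomiting that is recorded as an AE, the listings preserve the data, and the z values only gauge visibility. Two things remain. Neither document says that a vomit noted in the diary must be entered as an AE, and the preferred-term tables do not isolate the 30 minutes after a dose. The mention of summary statistics in 11.4 does not close the gap: it is tied to the listed classes, whereas the neighboring text on doses administered names the mean, SD, median, minimum and maximum explicitly.

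**Conclusion.** The point holds, within narrow limits. That 0 to 6 of 28 vomited doses share one class is arithmetic and rests on no assumption. How much the table could hide depends on rates the documents do not give. If per-dose vomiting is around 1 to 4% with modest clustering, a doubling between arms would be nearly invisible in the planned classes but clear in a count of infants with any vomited dose. At 5% versus 10% with ICC 0.1, the planned classes already show a difference. No estimate, endpoint or error rate changes. This is a low-importance improvement to a descriptive table, though that table is the only planned by-arm summary dedicated to vomiting within 30 minutes of a dose.

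**What to change.** In SAP 11.4, give vomited doses and partial doses their own rows. Report by arm, in the Safety population, the number and percentage of infants with 0 and with at least 1 such dose (for example classes 0, 1, 2–3, 4–6 and 7 or more), plus the mean and median count per infant. Keep the present classes for the breastmilk and water rows.

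The cost is one revised table shell. The data are already collected in the diary and exposure eCRF, and the vomit counts feed a planned listing. Making the change before unblinding avoids an ad hoc request later.
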